- To estimate incidence rates for hospitalised CAP among adults aged ≥60 years with underlying at-risk and high-risk medical conditions, in aggregate and for individual risk conditions within the limitations of the expected under ascertainment of hospital-based screening process and current diagnostic testing.

Additional 2019 Novel Coronavirus Disease 2019 (COVID-19)-related Exploratory Objectives

- To determine if the frequency of pneumococcal infection differs between hospitalised CAP patients with COVID-19 infection compared to those without COVID-19 infection, overall and stratified by age, sex, and pneumococcal risk status.
- Among the subset of hospitalised CAP patients with COVID-19 identified, to determine if the proportion who experience severe clinical outcomes (eg, intensive care unit [ICU] stay, mechanical ventilation, prolonged hospitalisation, and sequelae) differs between those with pneumococcal co-infection compared to those without pneumococcal co-infection, overall and stratified by age, sex, and pneumococcal risk status.
- Using a test-negative design to determine the VE of PCV13 against severe COVID-19 clinical outcomes among COVID-19 positive hospitalised CAP patients, overall and among immunocompetent persons only.
- To assess if pneumococcal carriage differs for those with current or past COVID-19 infection, overall and stratified by age, sex, and pneumococcal risk status.

Additional 2022 Respiratory Syncytial Virus (RSV) Exploratory Objective

• To determine the proportion of persons with RSV infection among adults 60 years of age and older presenting with CAP by testing saliva specimens using the PCR method.

Study design

This study is a low interventional, prospective, multicentre, hospital-based study involving adults 60 years of age and older hospitalised with CAP at participating sites. Hospital surveillance data will be used for incidence rates calculations. Vaccine effectiveness will be calculated using a TND. The approximate study duration will be 4 years.

Population

This study will prospectively enroll adults, aged 60 years and over, who are hospitalised with CAP in one of the study hospitals: Hospital Universitario de Móstoles, Hospital Universitario Fundación de Alcorcón, and Hospital Rey Juan Carlos de Móstoles (as of February 2022, additional sites may be included at a later date).

Variables

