Please see Section 10 for full listing. In summary, the screening step will collect demographic information, eligibility for the study, whether consented, any standard of care

PFIZER CONFIDENTIAL CT45-GSOP-RF152.0 Low-Interventional Study Protocol Template 05-Dec-2019 Page 11 of 70

(SOC) test results. If consent is given, then further data collection and enrolment would include: medical and vaccination history, smoking and alcohol use, details of current illness including all symptoms, treatment, severity score, vital signs and test results. At follow up, confirmation of CAP or alternative diagnosis, event disposition and vital status would be recorded at two visits: 30 and 180 days after hospital admission.

Data sources

Data will be collected from the hospital, including radiology and laboratory results, as well as primary care medical records.

Study size

The required sample size depends on the accrual of immunocompetent VT-CAP cases, the VE point estimate, percentage of individuals vaccinated, as well as other factors. Based on current estimates, the overall number of subjects to be enrolled is expected to be between 2,000 and 5,500 and required time for enrolment will be between 1.7 and 4 years, depending on the values for the parameters mentioned above and enrolment rates. See Section 12.1.2 for full information on these calculations. As the required number of enrolled subjects is highly dependent on the proportion of CAP subjects that have VT pneumococcal CAP and the proportion of the population vaccinated, the required sample size may be adjusted based on ongoing information from UAD testing results and vaccine exposure data if needed. An interim analysis will be conducted after accrual of 170 VT-cases but, given additional subjects may be needed to allow for adequate statistical power, at least 4 years of enrolment is planned.

Data analysis

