Vaccine Effectiveness will be calculated as follows. Odds of having received PCV13 for cases and controls will be constructed and compared using odds ratios (OR) and 95% Confidence interval (CIs). We will calculate VE as 1-OR x 100. In addition to constructing crude OR and VE estimates, we will also perform propensity score matching cases and controls using potentially confounding factors for VE, and then construct a conditional logistic regression to assess PCV13 and PPV23 VE. For the other study objectives, descriptive analysis will be carried out, presenting the absolute and relative frequencies of the qualitative variables and the main measures of centralization and dispersion in case of quantitative variables. CAP incidence rates per 100,000 inhabitants of the study age group will be assessed based on CAP events captured on screening log during the recruitment period in the participating sites. Methodologies for the statistical analyses of the data collected in this study are outlined here and will be provided in detailed in the full study protocol and statistical analysis plan (SAP).

Milestones

Milestone	Planned date
Completion of feasibility assessment	Q2 2020
Start of data collection, First Subject First Visit (FSFV)	March 2021
End of data collection, Last Subject Last Visit (LSLV)	Q1 2025
Interim analysis	After approximately 170 immunocompetent VT- CAP cases available for analysis [~Q2 2022]
Study results	Q2 2025
Final study report	Q3 2025

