An interim analysis is planned after accrual of 170 VT-cases but depending on the VE point estimate, the proportion of CAP cases that are vaccine serotype, and the frequency of PCV-13 vaccination in the study population, additional subjects may be needed to allow for adequate statistical power. On this basis, approximately 4 years of enrolment is planned.

If the anticipated PCV20 is approved during the enrolment of cases for VE analysis as expected (projected to be in use no sooner than late 2022), subjects with PCV20 exposure will be excluded from the cases and the controls for the PCV13 VE analysis. Initial PVC20 use is expected to primarily involve those aging into the over 60 age group, and substantial number of persons with a history of PCV13 vaccination are expected to remain in that age group population.

Laboratory testing. The Central laboratory will conduct BinaxNOW[®] (Alere, Walthman, MA) and the serotype-specific UAD1 and 2 assays (Pfizer, Inc) to test urine samples from all enrolled participants as the study-related procedures. Results from SOC tests performed on enrolled subjects will be also collected, including respiratory, blood, and pleural fluid cultures and urine pneumococcal antigen testing. All pneumococcal isolates will undergo serotyping.

Pneumococcal Carriage and RSV infection assessments. In addition, patients at selected study sites will provide a saliva sample to test for pneumococcal carriage and RSV infection but, if they decline this procedure at the time of collection, they will not be excluded from the study. Samples will be processed for pneumococcal detection by the standard, conventional culture diagnostic approach and molecular methods. RSV will be detected by molecular methods only.

Incidence assessment. Population-based incidence of CAP will also be estimated in this study. Nearly all CAP hospitalisations in the surveillance regions are expected to involve the study hospitals. Every effort will be taken to identify all pneumonia patients admitted to

PFIZER CONFIDENTIAL CT45-GSOP-RF152.0 Low-Interventional Study Protocol Template 05-Dec-2019 Page 30 of 70

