J11.00 J11.01	Influenza due to unidentified influenza virus with unspecified type of pneumonia. Influenza due to unidentified influenza virus with other respiratory manifestations. Influenza due to unidentified influenza virus with specified pneumonia.
J11.08	
J13	Pneumonia due to Streptococcus pneumoniae
J14	Pneumonia due to Hemophilus influenzae
J15	Unspecified bacterial pneumonia
J16	Pneumonia due to other infectious organisms, not elsewhere classified
J17	Pneumonia in diseases classified elsewhere
J18	Bronchopneumonia, unspecified organism

Table 5.Codes for Hospitalised Pneumonia Under ICD-10

a. The ICD codes in this column as well as J1100, J129, 5100, 5109, and 5130 will be used to retrospectively screen for missed CAP events to ensure completeness of surveillance.

For this study surveillance region, we expect approximately 1800 all-cause CAP patients in the age group of the study are hospitalised yearly based on 2018 data. This would represent 162 PCV13-type cases per year overall considering 9% of VT-CAP cases as per the CAPA study¹ and 648 PCV13-type cases in 4 years of expected duration of the study. Approximately, 36% of CAP admissions are expected to be immunocompromised persons, so we expect ~104 immunocompetent CAP cases annually (~416 over 4 years).²⁰ The following table (Table 6) estimates accrual of cases and controls for the VE analysis for immunocompetent subjects varying the key inputs. For these calculations, 2.5% alpha was used to split alpha allocated between interim analysis and final analysis (ie, 2.5% to each analysis).

Scenario input vari	.,	Vaccine Coverage Among Controls	Projected Vaccine Effectiveness	Vaccinetype (VT) Serotype Prevalence	Case:Control Ratio based on VT Serotype Prevalence	Needed Cases	Expected non-VT Controls	Total Evaluable subjects	Enrolled,⁵ n	% CAP inpatients enrolled	CAP inpatients needed, ^c n	Years to Enroll ^d
Expected	1	15%	70%	9%	1:10	117	1165	1282	1349	70%	1928	1.7
VE	2ª	15%	60%	9%	1:10	170	1692	1862	1960	70%	2800	2.4
	3	15%	50%	9%	1:10	259	2584	2843	2993	70%	4275	3.7
_	4	15%	40%	9%	1:10	427	4261	4688	4935	70%	7050	6.1
% CAP	5	15%	60%	7%	1:13	167	2160	2327	2449	70%	3499	3.0
VT	6	15%	60%	11%	1:8	173	1380	1553	1635	70%	2335	2.0
	8	15%	60%	13%	1:7	176	1224	1400	1474	70%	2105	1.8
% Vax	9	10%	60%	9%	1:10	252	2516	2768	2914	70%	4162	3.6
% VdX	10	20%	60%	9%	1:10	129	1283	1412	1486	70%	2123	1.8
90% Power	11	15%	60%	9%	1:10	208	2070	2278	2398	70%	3426	3.0

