In conclusion, assuming 9% VT-CAP, Scenario 1 sample size would be reached in 1.7 years after enrolling 1349 immunocompetent subjects (~2107 subjects overall), Scenario 2 (base case) in 2.4 years after enrolling 1960 immunocompetent subjects (~3063 subjects overall), and Scenario 3 in 3.7 years after enrolling 2993 subjects (~4,677 subjects overall). An increase in percentage of cases that VT-serotype to $\geq 11\%$ or the vaccinated proportion to 20% would reduce the time to accrue the needed cases for the interim analysis to 2 years or less. Lower proportion of VT-serotypes, lower VE point estimate, lower percentage of PCV13-vaccinated persons, or lower number of patients enrolled or subjects with valid urine specimens could all increase the time to achieve the needed number of vaccine serotype CAP cases. As the required number of enrolled subjects is highly dependent on the proportion of CAP subjects that have VT pneumococcal CAP and the proportion of the population vaccinated, the required sample size may be adjusted based on ongoing information from UAD testing results and vaccine exposure data if needed. An interim analysis will be conducted after accrual of 170 VT-cases (scenario 2 above), but, given additional subjects may be needed to allow for adequate statistical power, 4 years of enrolment is planned, which would bring the number of subjects enrolled to 5,400 (based on 1,800 potential subjects annually and 70% enrolled).

If the anticipated PCV20 is approved during the enrolment of cases for VE analysis as

expected (projected to be in use no sooner than late 2022), subjects with PCV20 exposure will be excluded from both the cases and the controls for the PCV13 VE analysis. We expect substantial number of persons with a history of PCV13 vaccination to remain in the population in this age group and, thus, event accrual for VE analysis would not be significantly impact immediately following the PCV20 launch.

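### The 5,400 enrolment total does not follow from its own inputs (they give 5,040), and the milestones leave about 3.2 to 3.6 years of enrolment, not 4

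*Protocol*

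**What the plan says.** Protocol 12.1.2 closes its sample size argument with 4 years of enrolment, "which would bring the number of subjects enrolled to 5,400 (based on 1,800 potential subjects annually and 70% enrolled"). The Summary says "at least 4 years of enrolment is planned" and section 9.1 says "approximately 4 years of enrolment is planned". Elsewhere the same figure describes the whole study: "The approximate study duration will be 4 years" (Protocol 3 and 9.1, and SAP 2.2). Protocol 12.1.2 also multiplies annual vaccine-type cases by the 4-year study duration to project 648 cases, about 416 of them immunocompetent.

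The milestone table gives March 2021 for "Start of data collection, First Subject First Visit (FSFV") and Q1 2025 for "End of data collection, Last Subject Last Visit (LSLV"). Visit 3 falls 180 to 195 days after admission (Protocol 6 and 10.5).

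On what is needed, "The following table (Table 6) estimates accrual of cases and controls for the VE analysis for immunocompetent subjects varying the key inputs". The text adds "Scenario 3 in 3.7 years after enrolling 2993 subjects (~4,677 subjects overall"). The overall enrolment range is 2,000 to 5,500 in 1.7 to 4 years (Protocol 3 and 12.1.2; SAP 4.1).

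**The concern.** A reader who multiplies the two printed inputs by 4 years does not get the printed total. A reader who lays the milestones against the visit schedule finds no room for 4 years of enrolment. Either way, the section that justifies the study size describes more accrual than the plan delivers.

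The 4 years is there for a reason. The protocol plans it because subjects beyond the 170-case base case may be needed for adequate power. What shrinks is therefore the margin kept for a lower vaccine effectiveness (VE), lower PCV13 coverage or lower enrolment.

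**Working it through.** **Inputs.** Protocol 12.1.2, with Table 6 and its notes: 1,800 admissions a year; 70% enrolled; 36% immunocompromised, so 64% immunocompetent (about 1,150 a year); 9% vaccine-type (VT); 5% without a valid specimen; 1:10 cases to controls. Dates are from Protocol 5, visit timing from Protocol 6.

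**1. The total.**
- 1,800 x 0.70 x 4 = 5,040. The stated 5,400 is 360 higher (360/5,040 = 7.1%).
- To reach 5,400 would take 75% enrolled (5,400/7,200), about 1,929 admissions a year (5,400/2.8), or 4.29 years (5,400/1,260). None of these is stated.
- The 5% specimen allowance does not explain it. Table 6 already counts those subjects as enrolled, and 5,040/0.95 is only 5,305.
- The rest of the section does reproduce. Scenario 2: 1,960/0.64 = 3,063 overall and 2,800/1,150 = 2.4 years. Scenario 3: 2,993/0.64 = 4,677 and 4,275/1,150 = 3.7 years.
- The upper bound of 5,500 would need 5,500/1,260 = 4.37 years.

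**2. The enrolment window.**
- Shortest: 1 January 2025 minus 195 days = 20 June 2024; from 31 March 2021 that is 3.22 years.
- Longest: 31 March 2025 minus 180 days = 2 October 2024; from 1 March 2021 that is 3.59 years.
- First to last visit spans 3.76 to 4.08 years, so 4 years does match the study duration.
- Four full years of enrolment from March 2021 would put the last visit between 28 August and 12 October 2025.

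**3. The 648 and 416 projections.** These are 162 x 4 and 104 x 4, so they treat study duration as accrual time. Over the window the same annual figures give 162 x 3.22 to 3.59 = 522 to 581, and 104 x 3.22 to 3.59 = 335 to 373. Both sets count all admissions, before the 70% and 5% factors.

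**4. Yield of the window at base rates.**
- Enrolled: 1,260 x 3.22 to 3.59 = about 4,060 to 4,520.
- Evaluable VT cases, overall: 1,260 x 0.95 x 0.09 = 107.7 a year, so 347 to 387.
- Evaluable VT cases, immunocompetent: 107.7 x 0.64 = 68.9 a year, so 222 to 247 (276 in a full 4 years).

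**5. Cases needed and power.** The Fleiss formula with continuity correction, 1:10, 80% power and two-sided alpha 0.025 gives 169.1, 258.3 and 251.5 cases for Scenarios 2, 3 and 9. Table 6 prints 170, 259 and 252.

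| Scenario | Needed at 0.025 | Needed at 0.05 | Power, immunocompetent, 0.025 | Power, immunocompetent, 0.05 | Power, overall, 0.025 |
|---|---|---|---|---|---|
| 2 (VE 60%, coverage 15%) | 170 | 140 | 93-96% | 97-98% | above 99% |
| 3 (VE 50%, coverage 15%) | 259 | 214 | 71-78% | 82-87% | 93-96% |
| 9 (VE 60%, coverage 10%) | 252 | 208 | 72-79% | 84-88% | 94-97% |

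Power is at 222 to 247 cases (immunocompetent) and 347 to 387 cases (overall). In a full 4 years (276 cases), immunocompetent power at 0.025 would be about 83% for Scenario 3 and 85% for Scenario 9.

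Scenario 12 (50% enrolled) needs 3,920/1,150 = 3.4 years, so as printed it fits only the longer end of the window.

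**The case against.** The tempting stronger reading is that the shortened window leaves the study underpowered. The documents do not support it, for three reasons.

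- **Alpha.** The shortfall in Scenarios 3 and 9 exists only at 0.025, a split made to share error between an interim and a final analysis. SAP 7 drops the interim analysis of effectiveness, and SAP 6.1.1.2 uses two-sided 0.05 for the matched analyses. At 0.05 both scenarios are met even in the shortest window. This stands, with a caveat: SAP 2.2 still prints 0.025 and the protocol still plans the interim, so the operative alpha is unreconciled.
- **Population.** The primary objective covers all subjects as well as immunocompetent ones, and the overall analysis has ample cases. This stands, although Protocol 12.5 sets the case target on immunocompetent cases.
- **Role of the total.** No row of Table 6, case target or power figure uses 5,400, and the protocol allows the sample size to be adjusted. This limits the consequence but does not make the sentence correct.

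It can also be said that the milestones are planned dates given to the month or quarter, and that 1,800 a year rests on 2018 data. A third hospital and non-residents have since been added to raise enrolment, and COVID-19 could halt it. Accrual could therefore move either way, and the yields above are illustrative.

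The dates are a different matter. The range already allows the most favourable reading of each milestone. Visit 3 may be done by record review, but it records vital status at day 180, so the follow-up time is still needed. Approximately 4 years in section 9.1 is elastic; at least 4 years in the Summary is not.

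**Conclusion.** Both inconsistencies hold. The stated total exceeds what its inputs give by 360 subjects (7%), and the documents do not show whether the total or an input is the wrong figure. The milestones and the day-180 visit allow about 3.2 to 3.6 years of enrolment against a planned 4, apparently because study duration and enrolment period have been treated as the same thing.

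The practical effect is limited. The base case needs 2.4 years and is not at risk. Scenarios 3 and 9 fall below 80% power only among immunocompetent subjects at alpha 0.025, and at the longest window Scenario 9 misses by little (247 cases against 252). At 0.05 they are met. This rests on constant accrual at the protocol's base rates, 9% vaccine-type prevalence and a 1:10 ratio. Severity is minor to moderate: stated figures need correcting, and the base case is unaffected.

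**What to change.** 1. Replace 5,400 with 5,040, or correct the printed input if another enrolment rate or admission count was meant.
2. Bring the 5,500 upper bound (Protocol 3 and 12.1.2; SAP 4.1) and the 648 and 416 case projections (Protocol 12.1.2) into line with the result.
3. State whether 4 years is study duration or enrolment, and use it in one sense throughout.
4. Then choose one of two options:
   - (a) Restate enrolment as about 3.2 to 3.6 years, with its yield of about 4,060 to 4,520 subjects, and say which Table 6 scenarios are reached at base rates.
   - (b) Keep 4 years of enrolment and move the last visit to about late August to mid-October 2025, with the reporting milestones.
5. State which alpha the accrual targets use, reconciling Protocol 12.1.2 and 12.4.1 and SAP 2.2 with SAP 6.1.1.2 and 7.

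All of this except option (b) is wording in the protocol and SAP and leaves conduct unchanged. Option (b) delays the study results (now Q2 2025) and the final report (now Q3 2025).

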12.1.3. Analysis Populations

12.1.3.1. Vaccine Effectiveness CAP Population (Primary Analysis Population)

The Primary Analysis Population will include all participants who:

- 1. Meet all inclusion and exclusion criteria.
- 2. Have a final diagnosis consistent with CAP (CAP-Radiologically Confirmed; CAP-Not Radiologically Confirmed or CAP-no chest radiology done).
- 3. Meet the definition of either case or test-negative control from Section 12.1.1.
- 4. Have \geq 5 combined years of pneumococcal vaccination history available.
- 5. Did not receive any pneumococcal vaccination ≤30 days prior to urine sample collection.
- 6. Have not received PCV20 if available in surveillance region during study.

This population will be analysed overall and restricted to immunocompetent subjects which will be all subjects not noted to the immunocompromised in Table 7.

Table 7.Categorization of Risk Factors by Immunocompetence³

Risk factor	Spain's Categorization		
Age	60 +		
Diabetes mellitus	immunocompetent		
Alcoholism	immunocompetent		
Chronic heart disease	immunocompetent		
Chronic liver disease	immunocompetent		
Chronic lung disease	immunocompetent		
Smoking	immunocompetent		
Congenital or acquired asplenia	immunocompromised		
Cerebrospinal fluid leak	immunocompetent		
Cochlear implant	immunocompetent		
Congenital or acquired immunodeficiencies	immunocompromised		
HIV infection	immunocompromised		
Chronic renal failure	immunocompromised		
Nephrotic syndrome	immunocompromised		
Leukemia	immunocompromised		
Hodgkin's disease	immunocompromised		
Lymphoma	immunocompromised		
Generalize malignancy	immunocompromised		
Iatrogenic immunosuppression	immunocompromised		
Solid organ transplant	immunocompromised		
Multiple myeloma	immunocompromised		
Antineoplastic chemotherapy	not specified		
Occupational risk with exposure to metal fumes	not specified		
Bone marrow transplantation	immunocompromised		
Neurologic diseases (eg, cerebral palsy and seizures)	not specified		
Prior IPD	immunocompetent		

These populations will serve as the primary analysis population for the primary endpoint and the secondary objective of calculating VE for PPV23.

³ Official Regional Immunisation Programme in the Community of Madrid, 2019.

12.1.3.2. Five-year PPV23-naïve Population

The Five-year PPV23-naïve Population is a subset of the Primary Analysis Population and will include participants from the Primary Analysis Population that have not received PPV23 within the last 5 years. To better understand the impact of PPV23 use on PCV13 VE, the primary endpoints will be analysed in this population in addition to the primary analysis population as a sensitivity analysis.

12.1.3.3. Radiologically Confirmed CAP Population

The VE populations endpoints will be analysed in this population as a sensitivity analysis to determine the impact of requiring radiographic confirmation for the diagnosis of CAP. All requirements will be the same as the "All CAP" population but the events must have a final diagnosis of "CAP-radiologically confirmed" consistent with the definition provided in Section 10.2.

